### **Sample Size Adjustment:**

To further enhance the reliability of our results and address the concern regarding sample size, we have considered increasing the sample size slightly. By recruiting approximately 60 patients per group, we aim to provide against dropout-related issues and enhance the generalizability of our findings. This adjustment allows for a more robust study design without compromising the practicality of recruitment within our study timeline and available resources.

### **Details of the interventions (not procedures) involved in the research:**

The study involves the application of two topical treatments, HM Gel and BS Ointment, to the respective treatment groups. The application of these treatments will follow established protocols. The study does not involve any invasive procedures.

The administration of the assigned treatments will be administered in routine clinical practice following the surgical procedure, either episiotomy or cesarean section, and continue for a period of two weeks. During this period, the participants will be instructed on the proper application of the treatments. The application frequency and dosage will be as follows:

- Hydrophilic Methacrylate Gel (HM Gel): Participants in the experimental group will be instructed to apply HM Gel to the surgical site two times a day, in the morning and evening, for the duration of the two-week treatment period.
- Beta Sitosterol Ointment (BSO): Participants in the control group will be instructed to apply BSO to the surgical site two times a day, in the morning and evening, also for the duration of the two-week treatment period.
- The application process will be explained to each participant, emphasizing the importance of consistent and thorough application. Adherence to the treatment regimen will be monitored through regular follow-up visits. These follow-up visits will coincide with the baseline assessment, occurring at recruitment, and subsequent visits at Day 5 and Day 12 postpartum. The administration of the assigned treatments will commence immediately following the surgical procedure, either episiotomy or cesarean section, and continue for a period of two weeks. During this period, the participants will be instructed on the proper application of the treatments. The application frequency and dosage will be as follows:
  - Hydrophilic Methacrylate Gel (HM Gel): Participants in the experimental group will be instructed to apply HM Gel to the surgical site two times a day, in the morning and evening, for the duration of the two-week treatment period.

## HMC RESEARCH PROTOCOL

- Beta Sitosterol Ointment (BSO): Participants in the control group will be instructed to apply BSO to the surgical site two times a day, in the morning and evening, also for the duration of the two-week treatment period.
- The application process will be explained to each participant, emphasizing the importance of consistent and thorough application. Adherence to the treatment regimen will be monitored through regular follow-up visits. These follow-up visits will coincide with the baseline assessment, occurring at recruitment, and subsequent visits at Day 5 and Day 12 postpartum.
- Phone Call Reminders by a trained staff to assess adherence of application. (Script is added in documentation in ABHATH)

### Follow-Up Phone Calls:

Phone call reminders will be made by trained staff to assess treatment adherence. Specific timepoints for planned follow-up phone calls are Day 3 and Day 7.

These follow-up calls will serve to reinforce proper application, address any concerns, and ensure consistent adherence to the treatment regimen. The detailed script in the ABHATH documentation provides guidance for the phone call reminders.

### **Data/samples (bio-specimens/information) collected at each time point and why:**

Data collection will involve both objective measures and participant-reported outcomes. The data to be collected at each time point include:

- Wound healing progress: This objective measure will assess the healing process of the scars over time.
- Scar appearance: This will be evaluated using the Patient and Observer Scar Assessment Scale (POSAS), a validated tool designed to assess cosmetic outcomes.
- Pain levels: Standardized pain scales will be employed to assess pain levels, comparing the effectiveness of the treatments in alleviating pain.
- Patient satisfaction: Questionnaires will be used to gather information on patient satisfaction with the treatment outcomes.
- These data will provide valuable insights into the assessment of the effectiveness of the treatments and their impact on wound healing, scar appearance, pain management, and patient satisfaction.

### **Risks to participants in the proposed research and anticipated benefits to clinical/health outcome:**

As described, the proposed research involves the use of topical treatments (HM Geland BS Ointment) for wound healing and scar management. Both treatments are generally considered safe, and no invasive procedures are involved in the study.

## HMC RESEARCH PROTOCOL

The anticipated benefits to participants include improved wound healing and scar appearance, reduced pain levels, and potentially enhanced patient satisfaction with the treatment outcomes. By comparing the two treatments, the study aims to provide evidence-based recommendations for scar management after episiotomy and cesarean section procedures, which may improve patient care and outcomes in these surgical contexts. The risks to participants are minimal, and the potential benefits to clinical and health outcomes make the research reasonably worthwhile.

### 7. Study Population and Study Setting/ Location

This study will be a prospective, randomized, controlled clinical trial. Participants will be randomly assigned to either an experimental group receiving HydrophilicMethacrylate Gel (HM Gel) or a control group receiving Beta Sitosterol Ointment(BS Ointment). The randomization process will utilize a stratified randomization method based on age and BMI to ensure balanced representation of different age groups and BMI categories within each treatment group.

#### **Stratification:**

In our study, we will indeed have two distinct groups of patients: those who have undergone episiotomy and those who have undergone cesarean section. We recognize that the type of surgery is a potentially important factor that should be considered in the randomization process to ensure balanced representation of both surgical groups in each treatment arm. To address this concern, we will implement a stratified randomization approach that accounts for the type of surgery as a stratification factor. Specifically, during the randomization process, participants will be stratified into two groups: the episiotomy group and the cesarean section group. Within each of these strata, randomization will be performed independently to allocate participants to either the experimental group receiving Hydrophilic Methacrylate Gel (HM Gel) or the control group receiving Beta Sitosterol Ointment (BS Ointment). In our final study report, we will provide a detailed description of the randomization process, including how participants were allocated to treatment groups within each stratum.

#### **Blinding:**

We will be blinding the tube ointments to ensure impartiality in the assessment of efficacy between the two treatments. This adjustment will enable us to minimize potential biases and ensure the integrity of our results.

The ointment tubes will be packaged in identical outer packaging, such as opaque boxes, to conceal any distinguishing features.

This approach will ensure that the participants nor the assessors of wound know which

## HMC RESEARCH PROTOCOL

ointment is being used.

In addition, to minimize bias during data analysis, the data analysts will be blinded to the treatment allocation until the analysis is completed.

### **Informed Consent:**

Informed consent is a crucial part of this study. We will carefully explain the details of the research to each participant, ensuring they have a comprehensive understanding of what is involved. This includes information about the nature of their participation, possible risks, anticipated benefits, and their right to withdraw from the study. Additionally, as a token of appreciation for their valuable contribution, participants will receive a small encouragement gift. Our aim is to provide participants with all the information they need to make an informed decision about their involvement in the research.

### **Study Duration:**

The expected length of the study is one year (15/12/2023 - 01/11/2024), which includes participant recruitment, intervention, follow-up, and data analysis.

### **Study instruments :**

To ensure the validity and cultural appropriateness of the study instruments, we will review the available literature and consult with experts in the field to identify validated instruments that have been culturally adapted for use in Arabic and other commonly spoken languages in Qatar. If such instruments are available, we will incorporate them into our study. In the event that validated instruments are not readily available in the desired languages, we will try to undertake a careful process of cultural adaptation. This process will involve translation, back-translation, and cognitive interviewing to ensure that the instruments are linguistically and culturally appropriate for our participants.

### **Inclusion Criteria:**

Eligible participants for this study will be adult females aged 18 years and above, who have recently undergone episiotomy or cesarean section procedures. Specific inclusion criteria include:

1. Adequate reading and writing literacy.
2. Live term singleton pregnancy.
3. Mediolateral episiotomy without tear.
4. Absence of chronic systemic diseases that delay wound healing (e.g., coagulation disorders, diabetes, anemia (Hb) < 9 g/dl).
5. No history of previous injury, surgery, or visible lesions in the perineum (e.g., genital warts, hemorrhoids).

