### 6. Study Methodology

The proposed study is a prospective, randomized controlled trial (RCT) that aims to compare the effectiveness of two topical treatments, HM Gel (Hydrophilic Methacrylate Gel) and BS Ointment (Beta Sitosterol Ointment), in promoting the healing process of episiotomy and cesarean section scars. The study will include two groups: an experimental group receiving HM Gel and a control group receiving BS Ointment.

**Sample size calculation or justification of numbers:** A priori sample size calculation will be conducted to determine the required number of participants for adequate statistical power. This calculation will consider factors such as the expected effect size, desired level of significance, power of the study, and anticipated dropout rate. We aim to recruit enough participants to ensure the statistical validity and generalizability of the study results.

The sample size for this study was determined based on the desired level of statistical power (80%) and the significance level (0.05). Since no prior estimates of effect size were available, a moderate effect size was assumed. Using a two-sample t-test, the sample size per group was calculated to be 53 participants in patients with cesarean section. Considering rounding up to the nearest whole number, a total sample size of

106 participants was determined for the 2 groups of cesarean section, and the same number for patients (53) with episiotomy, a total of 106 participants was determined for the 2 groups of vaginal delivery with episiotomy. This sample size calculation ensures that the study will have sufficient power to detect meaningful differences in pain levels and wound healing outcomes.

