## HMC RESEARCH PROTOCOL

6. Does NOT have chorioamnionitis and/or postpartum endomyometritis
7. No manual removal of placenta.
8. No postpartum hemorrhage (PPH).
9. Absence of perineal hematoma.
10. Infant weight between 2500 and 4000 g.

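### One common inclusion list requires a mediolateral episiotomy of every participant, which contradicts the plan to enrol caesarean patients as half of the sample

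*Combined protocol and SAP*

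**What the plan says.** The Inclusion Criteria in section 7 begin with a population sentence covering adult women "who have recently undergone episiotomy or cesarean section procedures". The list that follows is introduced by "Specific inclusion criteria include" and runs to ten numbered items, without subheadings or any wording that ties an item to one type of surgery. Three items concern the perineum:

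- Item 3: "Mediolateral episiotomy without tear".
- Item 5: "No history of previous injury, surgery, or visible lesions in the perineum", with genital warts and hemorrhoids given as examples.
- Item 9: "Absence of perineal hematoma".

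Elsewhere the plan clearly expects caesarean patients. The sample-size text in section 6 states that "106 participants was determined for the 2 groups of cesarean section", and sets the same number for vaginal delivery with episiotomy. The Stratification paragraph in section 7 describes two kinds of patient, "those who have undergone episiotomy and those who have undergone cesarean section", and says that "participants will be stratified into two groups: the episiotomy group and the cesarean section group".

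**The concern.** Item 3 is a positive requirement: to satisfy it, a woman must have had an episiotomy. A caesarean patient ordinarily has not. The list therefore conflicts with the sentence that introduces it and with the sample-size plan.

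Eligibility is checked item by item at screening, and section 8 says that patients are recruited against these criteria. Staff then have two options. They can apply item 3 to everyone, in which case ordinary caesarean patients fail screening and one of the two surgical questions is not answered. Or they can pass over item 3 for caesarean patients, in which case those women are enrolled without meeting the written criteria.

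The second course brings a further uncertainty. Once item 3 is set aside by unwritten agreement, nothing says whether items 5 and 9 are set aside too. One screener might turn away a caesarean patient because of hemorrhoids while another enrols her, although the study wound is abdominal.

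**Working it through.** **1. Planned numbers (section 6, sample-size text).** The plan gives 53 per group for each surgery.

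- Caesarean: 2 × 53 = 106, which agrees with the stated figure.
- Episiotomy: 2 × 53 = 106, which also agrees.
- Total: 106 + 106 = 212. Caesarean share: 106 / 212 = 50%.

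The Sample Size Adjustment paragraph raises recruitment to about 60 per group but gives no total. Assuming that this applies to all four groups, the total is 4 × 60 = 240, the caesarean number is 2 × 60 = 120, and the share is again 120 / 240 = 50%.

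**2. Side check on the 53.** The plan states 80% power, a 0.05 significance level and a moderate effect, but neither a numerical effect size nor the sidedness. The normal approximation for n per group is 2(z₁ + z₂)² / d².

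- d = 0.50, two-sided: 2(1.960 + 0.842)² / 0.25 = 62.8, so 63 (64 with the t distribution).
- d = 0.50, one-sided: 2(1.645 + 0.842)² / 0.25 = 49.5, so 50 (51 with the t distribution).
- d = 0.55, two-sided: 2(1.960 + 0.842)² / 0.3025 = 51.9, so 52 (53 with the t distribution).

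The 53 can thus be matched with d of about 0.55, but the documents do not confirm that this was the assumption. Nothing here depends on it: 53 is used only as the planned number per group.

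**3. Can an ordinary caesarean patient meet each item?**

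| Items | Type of condition | Result for a caesarean patient |
|---|---|---|
| Population sentence | Either surgery | Admitted |
| 1, 2, 4, 6, 7, 8, 10 | Literacy, pregnancy, systemic disease, infection, placenta, haemorrhage, infant weight | None requires an episiotomy |
| 3 | Positive: an episiotomy must be present | Not met, unless she had both procedures |
| 5, 9 | Negative: perineal history, lesion or haematoma must be absent | Can be met, but concerns a site other than the study wound |

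Only item 3 excludes a woman because her delivery was by caesarean. On the literal reading, none of the 106 planned caesarean participants qualifies, apart from an unusual woman with both procedures.

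**4. Does another section cure it?** No. The five exclusion criteria do not qualify item 3. No separate caesarean list appears in the protocol text. The Stratification paragraph says how the two surgical groups are handled at randomisation, not which criteria apply to each. Section 10 says that randomisation will not be stratified and that type of surgery will be examined by subgroup. That is a separate inconsistency, but it too presupposes that caesarean patients are enrolled.

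**The case against.** The strongest reply is that the intention is plain. The population sentence names caesarean section, the sample size provides for it, and item 3 can be taken as specifying the type of episiotomy for those women who had one. On that reading caesarean patients are eligible and nobody would turn them away.

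This stands as far as intention goes. It does not cure the text: item 3 carries no such qualifier, and the sensible reading has to be supplied by the screener. It also leaves items 5 and 9 unresolved.

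A reader might infer several stronger things that the documents do not support:

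- *Half the trial cannot be enrolled.* The population sentence and the sample-size plan point the other way. Moreover, the intention-to-treat rule in section 10 keeps every randomised participant in the analysis, so an informal waiver would not by itself remove these women's data.
- *The perineal items are a further bar.* Items 5 and 9 are conditions of absence, which a caesarean patient can meet. They raise a question of relevance and could exclude some individuals, but they do not exclude the group.
- *The caesarean population is undefined.* Age, the seven items that are not perineal and the five exclusions still describe it.
- *A previous caesarean goes unrecorded.* This cannot be checked. Variables follow a data collection sheet that is attached to the protocol but not shown, and medical records are also reviewed.
- *Repeat scars need a covariate.* Enrolling first and repeat incisions is a legitimate broad choice, and the planned chi-square, Fisher, t and Mann-Whitney tests have no place for a covariate. Adding one would not resolve the contradiction either.

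**Conclusion.** The point holds as an internal contradiction. Item 3, as written and applied to all participants, makes ordinary caesarean patients ineligible, against the population sentence directly above the list and against the sample-size plan. The exposed share is 106 of 212 planned participants, or 50%. It remains 50% at about 120 of 240 if the figure of 60 per group applies to all four groups. That share measures how much of the trial rests on an unclear rule; it is not a forecast of patients lost. The conclusion assumes that a caesarean patient ordinarily has no episiotomy, and that the attached forms, which are not shown, do not already divide the criteria by surgery. If a form does so, the protocol text still needs to agree with it.

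**What to change.** Reconcile the Inclusion Criteria with the sample-size text in section 6 and the Stratification paragraph in section 7. Divide the list into criteria common to all participants and criteria that apply only to the episiotomy group. Item 3 belongs in the second set, and so do items 5 and 9 if that is what is intended; if they are meant to apply to caesarean patients as well, the text should say so. Change the screening form to match. Whether any criteria specific to the abdominal incision are needed is for the investigators to decide.

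The cost is a short protocol amendment and a revised form, with no extra patients and no change to the analysis. It is best done before screening begins. If caesarean patients have already been enrolled, the amendment should record how item 3 was applied to them.

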## HMC RESEARCH PROTOCOL

6. Does NOT have chorioamnionitis and/or postpartum endomyometritis
7. No manual removal of placenta.
8. No postpartum hemorrhage (PPH).
9. Absence of perineal hematoma.
10. Infant weight between 2500 and 4000 g.

### Exclusion Criteria:

1. Use of other supplements or medications for wound healing during the study.
2. Inability to apply the ointment correctly as per instruction.
3. Sensitivity or allergy to the ointment or its components.
4. Participants who have a history of adverse reactions to similar topical treatments.
5. Participants who are unable to comply with study procedures and follow-up visits.

Note : The assessment of participants use of other supplements or medications during the study will be conducted through a combination of self-reporting and verification during regular follow-up visits. Participants will be asked to disclose any additional supplements or medications they are using, and this information will be cross-checked with their medical records in Cerner. Additionally, healthcare providers will actively inquire about any changes in medication or supplementation during follow-up visits.

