### Subject Withdrawal/ Withdrawal of Consent

In this study, participants have the right to withdraw from the trial at any time without providing a reason. Withdrawal of consent will not affect their current or future medical care. Participants who decide to withdraw from the study will be informed that they are free to do so without any negative consequences. Their decision to withdraw will be respected, and their data collected up to the point of withdrawal will be retained and included in the analysis, unless they specifically request their data to be removed.

To ensure proper handling of participant withdrawal, the study team will clearly communicate the withdrawal process during the informed consent process. Participants will be provided with contact information for the study coordinator or principal investigator, who will be available to answer any questions or concerns related to the study or the withdrawal process.

If a participant decides to withdraw their consent, their study participation will be terminated immediately. Any unused investigational product (HM Gel or BS Ointment)will be collected, and no further assessments or interventions will be performed on the participant.

The reasons for withdrawal, if provided voluntarily by the participant, will be recordedto inform the study team of potential issues and ensure continuous improvement of the research process.

Participant confidentiality will be strictly maintained throughout the study and beyond. All data obtained from participants who withdraw their consent will be handled withthe utmost confidentiality and will not be disclosed in any study-related publications or presentations.

It is important to emphasize that participant withdrawal is entirely voluntary, and participants will be assured that their decision will not impact their relationship with the

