## HMC RESEARCH PROTOCOL

between the two treatment groups.

- **Secondary Outcome Analysis:**

For secondary outcomes, such as pain management, scar appearance, and patient satisfaction, we will use similar statistical methods. Pain management and patient satisfaction may be assessed using standardized pain scales and questionnaires, respectively. Depending on the distribution of the data, we will utilize t-tests or Mann-Whitney U tests to compare continuous variables and chi-square tests or Fisher's exact tests for categorical variables.

- **Intention-to-Treat (ITT) Analysis:**

The primary analysis will be conducted on an intention-to-treat (ITT) basis, including all randomized participants. This approach accounts for protocol deviations and maintains the randomization balance between the groups. Participants will be analyzed according to their allocated treatment group, irrespective of protocol adherence or completion.

- **Subgroup Analyses:**

We will perform subgroup analyses to explore potential effect modifiers, such as age, BMI, or parity, on the treatment outcomes. Interaction tests or stratified analyses may be employed to investigate the impact of these factors on the primary and secondary outcomes.

- **Statistical Software:**

All statistical analyses will be performed using a reputable statistical software package, such as SPSS or R. These software tools are widely used for data analysis and will provide reliable results for this study.

- **Statistical Significance:**

Statistical significance will be defined as a p-value less than 0.05. Results with p-values less than this threshold will be considered statistically significant, indicating a significant difference between the treatment groups.

- **Who Will Perform the Analysis:**

The data analysis will be carried out by qualified statisticians [name] (HMC biostatistician) with expertise in statistical methods. These individuals will be independent of the study's clinical team and will be blinded to the treatment allocation to ensure unbiased analysis.

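### Exclusion item 1 can be met only after randomisation, so applying it contradicts the all-randomised ITT analysis; the withdrawal section also both keeps and, read literally, withholds withdrawn participants' data

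*Combined protocol and SAP*

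**What the plan says.** **Eligibility.** In Section 7, Exclusion Criteria, item 1 is "Use of other supplements or medications for wound healing during the study". The note below the list says that assessment of such use "will be conducted through a combination of self-reporting and verification during regular follow-up visits", with a cross-check against the medical record, and that "healthcare providers will actively inquire about any changes in medication or supplementation during follow-up visits". Section 6 places the visits at recruitment, Day 5 and Day 12. Item 2 concerns inability to apply the ointment as instructed. Item 5 is "Participants who are unable to comply with study procedures and follow-up visits". Neither has a stated time of assessment.

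**Analysis set.** Section 10, Intention-to-Treat (ITT) Analysis: "The primary analysis will be conducted on an intention-to-treat (ITT) basis, including all randomized participants". The same paragraph adds that women are analysed in their allocated group regardless of adherence or completion.

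**Withdrawal.** The section on Subject Withdrawal/ Withdrawal of Consent says of those who withdraw that "their data collected up to the point of withdrawal will be retained and included in the analysis", unless they ask for removal. Later, in a paragraph on confidentiality, it says that all data from participants who withdraw consent "will not be disclosed in any study-related publications or presentations".

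**The concern.** An exclusion criterion normally decides who enters the trial. Item 1 instead describes something a woman does once she is in it. If staff act on it as an exclusion, a randomised woman leaves because of her behaviour after allocation. Turning to another wound product is plausibly more common when the wound is healing badly. Removal could then depend on the outcome, and the comparison would lose the protection that randomisation gives and that the ITT paragraph says it maintains.

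The withdrawal section raises a related problem for reporting. If withdrawn participants' data are analysed but may not appear in any publication, the analysed result and the publishable result would rest on different sets of women.

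**Working it through.** **1. Item 1 against the ITT rule.** Take a woman who is randomised, starts treatment, and is found at Day 5 to be using another wound product.

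- Under Section 7 she meets an exclusion criterion.
- Under Section 10 she is analysed in her allocated arm, whatever her adherence.
- No section says which rule prevails, and no per-protocol or modified ITT set is defined to which item 1 might apply.

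Section 6 counts the recruitment assessment among the follow-up visits. That does not rescue a screening reading: use in the course of the study, and changes in use, cannot be known at recruitment.

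**2. Items 2 and 5.** Both are worded as inability, which can be judged at enrolment. Section 8 says patients are recruited on the inclusion and exclusion criteria, which fits that reading. The note on follow-up checks covers only supplements and medications. The timing of items 2 and 5 is therefore unstated rather than wrong.

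**3. Withdrawal.** There are three rules: data up to withdrawal are kept and analysed; data are removed on request; data from those who withdraw consent are not disclosed in publications. Taken literally, the third prevents publication of a result that the first requires. Removal on request is the only explicit route out of the analysis set.

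**4. Size.** The plan gives no removal rate and no healing rate, so there is no figure of its own to reproduce. Inputs:

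- about 60 per group (Section 6, Sample Size Adjustment);
- 10% dropout (Section 6, Dropout Rate), borrowed only as a size: 0.10 × 60 = 6;
- 70% healed in both arms (assumed).

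*Worst case: six women removed, all unhealed, all from one arm.*

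- Untouched arm: 42/60 = 70.0%.
- Other arm: 42/(60 − 6) = 42/54 = 77.8%.
- Spurious difference: 7.8 points.
- Pooled proportion 84/114 = 0.737; SE = √[0.737 × 0.263 × (1/60 + 1/54)] = 0.083; z = 0.078/0.083 = 0.94, p about 0.35.

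*Same removal in both arms:* 42/54 − 42/54 = 0.

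*Milder assumptions, no true difference.* Let p be the true healing rate, e the fraction removed and q the healing rate among those removed. The observed rate is (p − e·q)/(1 − e). With p = 0.70 and q = 0.30:

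- e = 5%: (0.70 − 0.015)/0.95 = 72.1%.
- e = 15%: (0.70 − 0.045)/0.85 = 77.1%.
- Bias: 5.0 points.

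Over p = 0.60 to 0.80 and q = 0.30 to 0.40, with type I error from the normal approximation to the two-proportion test at 60 per arm before removals (nominal 0.05):

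| Removed, arm A vs arm B | Bias, points | Type I error |
|---|---|---|
| 5% vs 5%, or 10% vs 10% | 0 | 0.05 |
| 5% vs 15% | 2.5 to 6.2 | about 0.06 to 0.15 |
| 10% vs 20% | 2.8 to 6.9 | about 0.06 to 0.20 |

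*Headroom.* The calculated requirement is 53 per group. After the planned dropout, 60 − 6 = 54 remain, so one further removal per group reaches 53.

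**The case against.** The strongest reply is that Section 10 already settles the matter. It states the analysis rule, says that rule covers protocol deviations, and includes every randomised woman. The note to item 1 describes asking and cross-checking, not removing anyone. A reader might infer that the protocol orders such women out of the analysis. It does not: no section says so, and the accurate statement is that they could be dropped because the consequence of meeting item 1 is undefined. The reply does not dissolve the conflict, because staff who follow the eligibility list in good faith could drop a woman whom the analysis section requires.

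A reader might also count items 2 and 5 as post-randomisation exclusions. Their wording concerns capacity, and nothing ties them to follow-up, so the documents do not support that.

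On withdrawal, the non-disclosure sentence sits in a paragraph on confidentiality and may mean only that individual data are not disclosed. That reading is plausible, so it cannot be said that the published set will differ from the ITT set. The text should still say which meaning applies.

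On size, the 7.8-point case is constructed. The 10% in the plan is anticipated dropout, not exclusion for using other products, and nothing confines it to one arm. The 70% is assumed. Participants and assessors are to be blinded, which makes differential removal less likely. Even the worst case does not reach significance by itself at 60 per arm. All of this stands, and it makes the size conditional. That poor healing leads women to other products is likewise plausible but not documented.

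**Conclusion.** The contradiction between exclusion item 1 and the all-randomised ITT rule is real and should be settled before outcome data are seen, because it decides who enters the primary analysis. The supported claim is that randomised women could be removed for post-randomisation behaviour, not that they will be.

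The possible bias runs from zero, when removal is alike in both arms and there is no true difference, to 7.8 points in the assumed worst case. Under the milder unequal-removal assumptions it is about 2.5 to 6.9 points. All of these figures rest on assumed healing and removal rates, since the documents give none.

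Items 2 and 5 need only a statement of timing. The withdrawal section is inconsistent on a literal reading and needs one clarifying sentence.

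**What to change.** 1. **Section 7.** State that all exclusion criteria are applied at screening, before randomisation. Reword item 1 as current use, or stated intention to use, another wound-healing product at that time. Mark items 2 and 5 as screening judgements.
2. **Sections 7 and 10.** State that use of other products, poor application or missed visits after randomisation are recorded as protocol deviations, and that these women stay in follow-up and in the ITT analysis. This concerns follow-up and analysis only, not how such women are treated.
3. **Withdrawal section.** Limit the non-disclosure sentence to identifiable individual data. Retained data from withdrawn participants are then reported in de-identified aggregate unless removal is requested. Report the number of removals on request by arm.

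The cost is wording only. Keeping non-adherent women in may dilute the effect slightly, as ITT already intends. How healing outcomes missing after withdrawal enter the analysis is a separate question, and this reconciliation does not depend on it.
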